5.1.2. Secondary Objectives

The secondary objectives of this study are:

- Localized Atrial Capture: evaluate if during the rapid pacing phase of the two-stage septal pacing scheme (rapid pacing followed by a step-wise transition to slow-pacing) from multiple electrodes on the interatrial septum, local atrial capture can be observed during atrial fibrillation.
- AF Termination Scheme: evaluate if AF termination can be obtained using a dual-stage septal pacing scheme (rapid pacing followed by a step-wise transition to slow-pacing) from multiple electrodes on the interatrial septum.

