5.2.2. Secondary Endpoint(s)

To assess Localized Atrial Capture the following endpoints will be considered:

- The number of AF episodes in which local capture is recorded during atrial septal stimulation in at least one of the electrode positions
- The number of electrodes for which local capture is determined using pacing schemes with various pacing cycle lengths (PCL) for a duration of 10-30 seconds depending on when capture occurs, at the start of the scheme followed, if feasible, by slow pacing for 1.5 s at 180% AFCL, initiated by a single stimulus at 130% AFCL.
- The spatial extend of capture (assessed from the atrial electrograms recorded from the multipolar right atrial catheter and the multipolar coronary sinus catheter) to obtain local atrial capture obtained with septal pacing of AF, will be assessed off-line after the study procedure.

To assess whether AF termination can be obtained using a dual-stage septal pacing scheme, the surface ECG will be analyzed and the PCL and stimulation current used will be noted to measure the number of subjects in which the pacing scheme successfully terminates the AF episode.

6. Study Design

The AF Septal Pacing study is a non-randomized, non-controlled, acute, single-arm research study that will be conducted in up to three European centers.

Approximately 15 subjects with AF indicated for ablation of the pulmonary vein will be enrolled in the study. Participants will attend the Baseline visit and the Procedure visit. The baseline visit can be on the same day as the ablation procedure. Since it is an acute study, no follow-up visit will occur. The research procedure will be performed during an already scheduled ablation procedure. Subjects will be enrolled over a period of approximately 18 months.

The point of enrollment is the time when subject signs and dates the Informed Consent Form (ICF). At that point, the subject is considered included in the study.

Selection of subjects, treatment of subjects, and evaluation of study data are potential sources of bias. Methods incorporated in the study design to minimize potential bias include (but are not limited to):

- Patients will be screened to confirm eligibility for enrollment in accordance to the inclusion/exclusion criteria.
- Subject demographics will be collected at baseline on possible differences that may affect the primary objective.

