| Monitoring system. | Could be e.g. a stationary Bard EP recording system, a physiological recorder, such as the porti-system (TMSI) or any other electrophysiological monitoring system used in EP lab during the ablation procedure. | CE marked | Monitoring (one per site) | NO (CE marked used within approved indications) |

Pacing system: A clinical electrophysiological stimulator will be used to deliver the dual stage septal pacing protocol to pace and potentially terminate atrial fibrillation. The stimulator should offer four independent pacing channels, to be able to independently stimulate the four electrodes of the interatrial septal catheter. If no four-channel electrophysiological stimulator is available at the clinical study site, study site can request Medtronic reimburse a commercially available four channel electrophysiological stimulator (St. Jude Medical – EP4-Stimulator). The provided stimulator is to be used in accordance with this Clinical Investigation Plan and for this study only.

Pacing catheters: A multipolar (decapolar) Lasso catheters will be used to pace the interatrial septum. In acute animal studies, a Biosense-Webster Lasso Catheter was successfully used²³. Therefore, it is preferable to use the Lasso catheter in this study unless experiences in this human study support the use of another Lasso catheter such as the Achieve. The decapolar Lasso or Achieve catheter will be used according to standard clinical practice.

Monitoring Catheters: Standard electrophysiological recording according to standard clinical practice during AF ablation will be used. This includes the use of a decapolar coronary sinus (CS) electrophysiological recording catheter, and the use of a decapolar right atrial (RA) electrophysiological recording catheter.

Monitoring System: Atrial electrocardiograms will be recorded throughout the study procedure. Intra-atrial electrocardiograms will be recorded from the right atrial decapolar catheter, the coronary sinus catheter and the interatrial septal catheter. All signals will be recorded on the available electrophysiological recording system.

The products needed are already available at the site as standard material used for the routine clinical ablation procedure, for which the patient is indicated and referred to the site.

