Next, atrial fibrillation will be induced by rapid atrial pacing, gradually elevating the atrial pacing rate until 1:1 atrial capture is lost. AF cycle length will be determined by recording the atrial electrogram on the septum. Stimulation on the septum from all electrodes starts at the current defined above, using various pacing cycle length (PCL), being percentages of AFCL and will last for 10 to 30 seconds, depending on when capture occurs, followed, if feasible, by slow pacing using an interval of 130% of AF for one cycle followed by 1.5 second of 180% of AF Cycle length at maximum output which did not induce ventricular capture (20 mA or lower). Multiple PCLs will be used to start the pacing sequence. During each stimulation sequence, corresponding to each PCL, atrial capture at each recording electrode will be assessed. The optimal parameters for stimulation will be used to determine local capture for all electrodes.

When the subject will still be in AF after successful pulmonary vein isolation the ventricular capture tests will be performed first during atrial fibrillation (as described above for subject in sinus rhythm). Then, AF cycle length will be determined and

the two-stage atrial pacing scheme as described above will be performed. If delivery of the two-stage atrial pacing scheme either will not be feasible or not stop the AF, the subject will be externally cardioverted under deep sedation as would have been done as common practice at the end of the ablation procedure. Next, during sinus rhythm pacing thresholds and impedances on all septal catheter electrodes will be determined.

To assess if the two-stage pacing scheme can terminate AF, the surface ECG will be analyzed and PCL and stimulation current will be noted.

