AF Termination Scheme: evaluate if AF termination was observed during the experimental atrial septal pacing scheme from multiple electrodes on the interatrial septum. Acute procedural AF termination was defined as termination of AF to SR or a regular atrial tachycardia/flutter during the experimental pacing procedure without re-initiation of atrial fibrillation during the experimental pacing scheme.

AF termination will be described as the count and frequency of any AF termination
Subgroup descriptions and summary of atrial capture and AF termination will be done for:

- Atrial fibrillation group (SR vs AF group)
- Catheter type (Achieve vs. Lasso or other)
- Anatomical electrode position
- Atrial Cycle Length

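### AF termination is scored with no AF-free time required after the last stimulus, so a conversion lasting a second or two can count as a success

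*SAP*

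**What the plan says.** SAP 8.7.2 defines acute procedural AF termination as "termination of AF to SR or a regular atrial tachycardia/flutter during the experimental pacing procedure", subject to one exclusion: it must occur "without re-initiation of atrial fibrillation during the experimental pacing scheme". The result is then summarised in one line: "AF termination will be described as the count and frequency of any AF termination".

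Protocol 5.2.2 makes the endpoint the number of subjects whose AF episode the scheme successfully ends. On method it says only that "the surface ECG will be analyzed and the PCL and stimulation current used will be noted"; Protocol 10.3 says much the same. Neither section gives a time for which the converted rhythm must last.

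Protocol 5.1.2 and SAP 5.2 use *scheme* for the two-stage sequence of rapid and then slow pacing. Protocol 10.3 gives the timings. Stimulation "will last for 10 to 30 seconds, depending on when capture occurs, followed, if feasible, by slow pacing", with one interval at 130% of AFCL "followed by 1.5 second of 180% of AF Cycle length". Several pacing cycle lengths are tried in each subject.

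**The concern.** The objective is to learn whether pacing ends the AF episode. The exclusion looks for AF return only while the scheme is running, and the scheme closes with 1.5 s of slow pacing. AF that converts late in a sequence and returns just after the last pulse is not excluded by the wording. The same holds if that subject then goes on to the cardioversion that Protocol 10 and 10.3 describe.

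Two features widen the opening. Several sequences per subject combined with a count of any termination give each subject more than one chance to score a brief event. And SAP Tables 5 and 6, although titled as covering AF termination, list only capture outcomes: no termination field, no time of termination and no time of recurrence. A reader of the final report could not separate a conversion that lasted from one that did not.

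**Working it through.** The plan states no figure for this endpoint, so there is none to reproduce. The check is how much AF-free time the rule demands.

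**Inputs**
- Rapid phase: 10 to 30 s (Protocol 10.3).
- Transition: one interval at 1.3 × AFCL (Protocol 10.3).
- Slow phase: 1.5 s at 1.8 × AFCL (Protocol 10.3).
- AFCL: 100 to 400 ms, the field range in SAP Tables 5 and 6. This is a database range, not an expected distribution. The 200 ms row below is illustrative.
- Subjects: about 15 (Protocol 6).

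**Step 1. AF-free time required if AF converts at the switch to slow pacing**

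Window = 1.3 × AFCL + 1.5 s. Slow stimuli ≈ 1500 ms / (1.8 × AFCL).

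| AFCL (ms) | Transition (s) | Window (s) | Slow stimuli (approx.) |
|---|---|---|---|
| 100 | 0.13 | 1.63 | 1500/180 = 8.3 |
| 200 | 0.26 | 1.76 | 1500/360 = 4.2 |
| 400 | 0.52 | 2.02 | 1500/720 = 2.1 |

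**Step 2. Other conversion times.** A later conversion leaves a shorter window, approaching zero at the last stimulus. If slow pacing is not feasible, the window ends with the rapid phase. The whole sequence lasts from 10 + 1.63 = 11.63 s to 30 + 2.02 = 32.02 s, so about 32 s is the most one sequence can demand, and only for AF that converts at its first stimulus.

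**Step 3. The other reading of the sentence.** The SAP sentence uses both *procedure* and *scheme*. If *scheme* meant the whole series of sequences (Protocol 10.1 puts the study procedure at about 30 minutes), AF returning between sequences could disqualify a success. AF returning after the final sequence still would not. No reading supplies a window after the last stimulus of the series.

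**Step 4. Direction.** Adding an AF-free requirement to the existing rule can only remove cases from the count. Omitting it can therefore raise the count or leave it unchanged.

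**Step 5. Weight of one case.** 100/15 = 6.7 percentage points if 15 subjects are evaluable. SAP 8.1.4 keeps subjects without overdrive pacing in the per-protocol set, and the summary line names no denominator, so this depends on a choice that the SAP leaves open. With 12 paced subjects (assumed) it would be 100/12 = 8.3 points.

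**Illustration, counts assumed.** 4/15 = 26.7% (Clopper-Pearson 95% interval 7.8 to 55.1). If two of the four resumed AF at once, 2/15 = 13.3% (1.7 to 40.5).

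**The case against.** The best reply is that the definition already asks for something real. Conversion must be to sinus rhythm or a regular tachycardia/flutter, a purely paced rhythm is not sinus rhythm, and the SAP treats activity tied to the stimulus separately, as capture. Protocol 5.2.2 also speaks of the episode being successfully terminated, and a sensible reader of the ECG might not credit AF that is back within a second.

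This stands in part. A reader might infer that pacing-driven suppression necessarily scores as termination. The documents do not support that: a case with no unpaced organised beat before AF returns is disputable under the wording, not clearly a success, and nothing says that the rhythm must be read while stimuli are being delivered. But a brief genuine conversion followed by AF just after pacing does meet the SAP wording, and the general phrase in the Protocol does not override a specific definition.

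A reader might also infer that the count could not be set against the 29% termination seen in the computer model (Protocol 4.1). The documents do not say how the model defined termination, and no planned analysis makes the comparison, so nothing follows either way.

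It is also fair to say that the endpoint is secondary, descriptive, untested and evaluated only where feasible. That limits the weight of the point but does not remove it.

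**Conclusion.** The point holds as a gap in an endpoint definition. Followed literally, SAP 8.7.2 can count a conversion that needs to last only about 1.6 to 2.0 s if it begins at the switch to slow pacing, and less if it begins later. This rests on the documents' usual meaning of *scheme* and on AFCL within 100 to 400 ms. On the wider meaning, AF return after the last sequence still goes unscored.

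The direction is known but the amount is not. It is tempting to say that the reported frequency will be biased upward by some definite margin. The documents contain no recurrence data and no reference definition of lasting termination, so they show only that the count can be raised. With about 15 subjects, one or two such cases would visibly change a descriptive percentage. The primary objective, electrode stability, is untouched.

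**What to change.** Amend SAP 8.7.2 before the recordings are read:

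- Use one term for the window and state whether it means a single sequence or the whole series.
- Keep the present exclusion. Define termination as sinus rhythm or regular atrial tachycardia/flutter on the unpaced rhythm after the last stimulus of a sequence, read from the surface ECG and supported by the atrial electrograms. It must last a minimum AF-free interval counted from that stimulus. The sponsor sets and justifies the length; the documents give no basis for a particular value.
- Report conversion to sinus rhythm and to tachycardia/flutter separately, and list AF that returns inside the interval as transient suppression.
- State how a new sequence, re-induction, cardioversion or the end of the recording inside the interval is scored, for example as not assessable for sustained termination.
- Name the unit and denominator of the frequency.
- Add fields for termination and time to AF recurrence to SAP Tables 5 and 6.

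Most of the raw material should exist. Protocol 7.1 says "Atrial electrocardiograms will be recorded throughout the study procedure", and Protocol 10.5 lists ECG among the procedure data. It also says that episodes are stored, so an adequate stretch after pacing is not assured; hence the rule for recordings that end early.

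The cost is a rewritten definition, a few extra fields, one further read-out and possibly a less favourable count. The change affects scoring only, not how subjects are managed.

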8.8 Safety Evaluation

All adverse events (AE) will be reported. Summary description of all adverse event will be provided for each reported AE.

For serious adverse events (SAE), device related adverse events, and unanticipated adverse device effects (UADE) a detailed description will be provided.

8.9 Health Outcomes Analyses

No Health Outcome Analysis will be performed. This is an acute study, and no health outcome data were recorded.

8.10 Changes to Planned Analysis

Changes to the Planned Analysis need to be reviewed and agreed by the project statistician and the project scientist.

9. Validation Requirements

Matlab analysis validation. Results from Matlab code will be validated before use for the final analysis. A random subset of datasets will be both analyzed manually and automatically. Appropriate agreement between the manual reading and the automatic reading needs to be confirmed for validation. Alternatively, sample datasets with a known performance may be used for validation.

Statistical analysis validation. Results from the statistical analysis code will be validated before use for internal and external reporting. The analysis code will be reviewed for correctness before running the final analysis. A validation dataset will be created with known results. The analysis code is validated comparing consistency between the results of the know results and the results from the statistical analysis code. Results obtained from running the analysis code will be reviewed by the project statistician and the project scientist prior to use.

10. References

- Allessie, M., C. Kirchhof, et al. (1991). "Regional control of atrial fibrillation by rapid pacing in conscious dogs." Circulation **84**(4): 1689-1697.
- Carlson, M. D., J. Ip, et al. (2003). "A new pacemaker algorithm for the treatment of atrial fibrillation: Results of the Atrial Dynamic Overdrive Pacing Trial (ADOPT)." Journal of the American College of Cardiology **42**(4): 627-633.
- Daoud, E. G., B. Pariseau, et al. (1996). "Response of Type I Atrial Fibrillation to Atrial Pacing in Humans." Circulation **94**(5): 1036-1040.
- Ellenbogen, K. (2007). "Pacing therapy for prevention of atrial fibrillation." Heart Rhythm **4**(S84-87).
- Fukuta, H., T. Goto, et al. (2017). "Effects of catheter-based renal denervation on heart failure with reduced ejection fraction: a systematic review and meta-analysis." Heart Failure Reviews **22**(6): 657-664.

- Gillis, A. M., J. Koehler, et al. (2005). "High atrial antitachycardia pacing therapy efficacy is associated with a reduction in atrial tachyarrhythmia burden in a subset of patients with sinus node dysfunction and paroxysmal atrial fibrillation." Heart Rhythm **2**(8): 791-796.

Result table of stability performance assessment of the atrial septal ring electrodes. Data will be reported in the format of the table 2 or text below for all patients, and for each analyzed subgroup.

Table 2: stability performance

Variable	Data Count	Data missing	Median	Mean	Standard deviation	Minimum	Maximum
Pacing Threshold [mA]							
Pacing Pulse width [ms]							
Pacing Impedance [Ohm]							

Variable	Data Count	Data missing	Yes Count	Yes %	No Count	No %
Any capture [Yes, No]						
Stability capture [Yes, No]						
Ventricular capture [Yes, No]						

Result table of atrial septal pacing capture. Data will be reported in the format of the table 3 below or text for all patients, and for each analyzed subgroup.

Table 3: atrial septal pacing capture

Variable	Data Count	Data missing	Median	Mean	Standard deviation	Minimum	Maximum
Percentage Atrial Capture []							
AF cycle length [ms]							
AF coupling interval [ms]							

Data table description for baseline data (Table 1B).

Value	Field	Form	Key Fields
[ctrcode]	Ctr	StudyBaseline	Key1
[yes, no, na]	PatID	StudyBaseline	Key2
[18...100]	Age	StudyBaseline	
[DD-MMM-YYYY]	Date	StudyBaseline	
[male, female, na]	Gender	StudyBaseline	
[40 ...150]	Weight	StudyBaseline	
[100 ... 200]	Height	StudyBaseline	
[yes, no, na]	IC-signed	StudyBaseline	
[yes, no, na]	Inclusion_1	StudyBaseline	
[yes, no, na]	Inclusion_2	StudyBaseline	
[yes, no, na]	Inclusion_3	StudyBaseline	
[yes, no, na]	Inclusion_4	StudyBaseline	
[yes, no, na]	Exclusion_1	StudyBaseline	
[yes, no, na]	Exclusion_2	StudyBaseline	
[yes, no, na]	Exclusion_3	StudyBaseline	
[yes, no, na]	Exclusion_4	StudyBaseline	
[yes, no, na]	AA	StudyBaseline	
[yes, no, na]	SND	StudyBaseline	
[yes, no, na]	VA	StudyBaseline	
[yes, no, na]	AVJ	StudyBaseline	
[yes, no, na]	AVJ1	StudyBaseline	
[yes, no, na]	AVJ2	StudyBaseline	
[yes, no, na]	AVJ3	StudyBaseline	
[5 ... 50]	RAI	StudyBaseline	
[5 ... 50]	LAI	StudyBaseline	

Data table description for procedure data (Table 2B).

Value	Field	Form	Key Fields
[ctrcode]	Ctr	StudyBaseline	Key1
[yes, no, na]	PatID	StudyBaseline	Key2
[DD-MMM-YYYY]	Date	StudyBaseline	
[General, Sedation, na]	Anesthesia		
[parox, persist, permanent, na]	AF_treated	StudyBaseline	
[initial, redo, na]	AF_type	StudyBaseline	
[yes, no, na]	AF_Ablate_AF	StudyBaseline	
[text]	Catheter_name	StudyBaseline	
[text]	Catheter_model	StudyBaseline	
[text]	Catheter_sn	StudyBaseline	

Data table description for pacing capture analysis (Table 3B).

Value	Field	Form	Key Fields
[ctrcode]	Ctr	StudyProc	Key1
[patcode]	PatID	StudyProc	Key2
[modelname]	Catheter	StudyProc	
[AF, SR]	Rhythmprotocol	StudyProc	
[1 ... 10]	Electrode	StudyProc	
[locationcode]	Stimlocation	Scientist	
[uni, bipolar]	Stimmode	Scientist	
[0 ... 25]	Pacingthreshold	StudyProc	
[mA, V]	PacingThresholdUnit	StudyProc	
[0 ... 2000]	Impedance	StudyProc	
[yes, no, na]	AnyAtrialCapture	StudyProc	
[yes, no, na]	StableAtrialCapture	StudyProc	
[yes, no, na]	Ventcapture	StudyProc	
[0 ... 25]	VentCaptureThreshold	StudyProc	
[mA, V]	VentCaptureUnit	StudyProc	
[yes, no, na]	StablePosition	StudyProc	

Data table description for electrode configurations tested (Table 4).

Value	Field	Form	Key Fields
[ctrcode]	Ctr	StudyProc	Key1
[patcode]	PatID	StudyProc	Key2
[1 ...]	ElecConfig	StudyProc	Key3
[modelname]	AF Septal Catheter	StudyProc	
[1 ... 10]	StimElec1_1	StudyProc	
[1 ... 10]	StimElec1_2	StudyProc	
[locationcode]	StimLoc1	StudyProc	
[1 ... 10]	StimElec2_1	StudyProc	
[1 ... 10]	StimElec2_2	StudyProc	
[locationcode]	StimLoc2	StudyProc	
[1 ... 10]	StimElec3_1	StudyProc	
[1 ... 10]	StimElec3_2	StudyProc	
[locationcode]	StimLoc3	StudyProc	
[1 ... 10]	StimElec4_1	StudyProc	
[1 ... 10]	StimElec4_2	StudyProc	
[locationcode]	StimLoc4	StudyProc	
[Uni, bipolar]	StimMode	StudyProc	

Data table description for local AF capture and AF Termination taken from the CRF (Table 5).

Value	Field	Form	Key Fields
[ctrcode]	Ctr	StudyProc	Key1
[patcode]	PatID	StudyProc	Key2
[1 ... 10]	ElecConfig	StudyProc	Key3
[1 ...]	Experiment	StudyProc	Key4
[100 ... 400]	AFCL	StudyProc	
[100 ... 400]	AFIntervalPaced	StudyProc	
[AF, SR]	Rhythmprotocol	StudyProc	
[uni, bipolar]	Stimmode	StudyProc	
[0 ... 25]	Stimoutput	StudyProc	
[mA, V]	Stimunit	StudyProc	
[yes, no, na]	Localcapture	StudyProc	
[yes, no, na]	CaptureRA	StudyProc	
[yes, no, na]	CaptureSL	StudyProc	
[yes, no, na]	CaptureCS	StudyProc	

Data table description for local AF capture and AF Termination taken from the Matlab analysis of atrial EGMs (Table 6).

Value	Field	Form	Key Fields
[ctrcode]	Ctr	StudyProc	Key1
[patcode]	PatID	StudyProc	Key2
[1 ... 10]	ElecConfig	StudyProc	Key3
[1 ...]	Experiment	StudyProc	Key4
[100 ... 400]	AFCL	StudyProc	
[100 ... 400]	AFCIntervalPaced	StudyProc	
[AF, SR]	Rhythmprotocol	StudyProc	
[uni, bipolar]	Stimmode	StudyProc	
[0 ... 25]	Stimoutput	StudyProc	
[mA, V]	Stimunit	StudyProc	
[CS, RA, Septal]	SenseCatheter	Matlab	
[1 ... 20]	SenseElectrode	Matlab	
[yes, no, na]	CaptureAnalysis	Matlab	
[0...100]	Capture Percentage	Matlab
